4.2. Endpoints

4.2.1. Primary endpoints (safety)

The primary endpoint of the study is to assess safety in term of occurrence of solicited and unsolicited adverse events (AE). Occurrence of AE will be monitored by preplanned medical visits and blood tests (active surveillance) and by recording participant's reported AE (passive surveillance). This includes:

- A. Occurrence of solicited local AE signs and symptoms for 7 days following the vaccination
- B. Occurrence of solicited systemic AE signs and symptoms for 7 days following the vaccination

- C. Occurrence of unsolicited AE for 28 days following the vaccination
- D. Change from baseline for safety laboratory measures at different 2 days, 7 days, 2 weeks, 4 week, 8 weeks, 12 weeks and 24 weeks
- E. Occurrence of serious AE (SAE) during the whole study duration

Volunteers will undergo clinical follow up for AE for 24 weeks following completion of the vaccination regimen. SAEs will be collected throughout the study.

4.2.2. Secondary endpoints (immunogenicity)

The secondary endpoint for the study is the assessment of cellular and humoral immune response elicited by the vaccine at different time weeks after the administration of three different doses of vaccine, namely 5×10^{10} , 1×10^{11} and 2×10^{11} viral particles, either in adults and elderlies. This include:

- A. CLIA to quantify antibodies to SARS-CoV-2 S-protein (anti-S-Ab) at week 2, 4, 8, 12 and 24 in adults who receive either 5×10^{10} , 1×10^{11} and 2×10^{11} viral particles;
- B. CLIA to quantify antibodies to SARS-CoV-2 S-protein (anti-S-Ab) at week 2, 4, 8, 12 and 24 in elderlies who receive either 5×10^{10} , 1×10^{11} and 2×10^{11} viral particles;
- C. CLIA to quantify antibodies to SARS-CoV-2 N-protein(anti-N-Ab) at week 2, 4, 8, 12 and 24 in adults who receive either 5×10^{10} , 1×10^{11} and 2×10^{11} viral particles;
- D. CLIA to quantify antibodies to SARS-CoV-2 N-protein(anti-N-Ab) at week 2, 4, 8, 12 and 24 in elderlies who receive either 5×10^{10} , 1×10^{11} and 2×10^{11} viral particles;
- E. SARS-CoV-2 micro-neutralization assay to quantify neutralizing antibody activity to the virus at week 4 and 24 in adults who receive either 5×10^{10} , 1×10^{11} and 2×10^{11} viral particles;
- F. SARS-CoV-2 micro-neutralization assay to quantify neutralizing antibody activity to the virus at week 4 and 24 in elderlies who receive either 5×10^{10} , 1×10^{11} and 2×10^{11} viral particles;
- G. Ex vivo IFN γ ELISpot responses to SARS-CoV-2 S-protein at week 2, 4, 8, 12 and 24 in adults who receive either 5×10^{10} , 1×10^{11} and 2×10^{11} viral particles
- H. Ex vivo IFN γ ELISpot responses to SARS-CoV-2 S-protein at week 2, 4, 8, 12 and 24 in elderlies who receive either 5×10^{10} , 1×10^{11} and 2×10^{11} viral particles

4.2.3. Exploratory endpoints

The exploratory objectives of this study are to provide preliminary evidence on kinetics of immune response for 3 doses (namely 5×10^{10} , 1×10^{11} and 2×10^{11} viral particles) of GRAd-COV2 either in healthy adults or in elderlies. Kinetics will be described as the variation of humoral and cellular immune response at time of enrollment and eventually at week 2, 4, 8, 12 and 24 after vaccination in each arm. Several T cells assay will be performed to identify T cell subset mainly involved in the response to vaccination and to evaluate their polyfunctionality and phenotypic profile. Level of Neutralizing antibodies (nAb) to GRAd32 will be measured in serum at time of enrollment, 4 and 24 weeks after vaccination to evaluate any potential impact on vaccination efficiency. A correlation between humoral and cellular immune response will be evaluated. Within-the-cohort comparisons will be carried out to assess difference in immune response according to different doses in the same population. Across-the-cohort comparison will be carried out to assess whether elderlies and adults have different pattern of immune response after vaccination at different end points.

4.2.4. Milestones

We expect to start enrollment within 4 weeks after final study approval. Eventual milestones include:

- A. DSMB authorizes ARM1 group B and ARM2 Group A
- B. DSMB authorizes ARM2 group B and ARM3 Group A
- C. DSMB authorizes ARM3 group B
- D. DSMB revises 4-week safety of whole Arm-1. DSMB authorize enrollment in ARM4 Group A.

- E. DSMB authorizes ARM4 Group B and ARM5 Group A
- F. DSMB authorize ARM5 Group B and ARM6 Group A
- G. DSMB authorize ARM6 Group B

4.2.5. Deliverables

- 1. Within five months after the study approval a report on safety and immunogenicity at 4 weeks for Adult-Cohort will be developed; this report will include:
 - a. an analysis of safety issue in the three adults-arms
 - b. pivotal consideration used for authorizing enrollment in the Elderlies-Cohort
 - c. a preliminary analysis of immunogenicity in the three adults-arms aimed at identifying the most convenient doses to be used in the eventual phase 2/3 trial.
- 2. Within seven months after the study approval a report on safety and immunogenicity at 4 weeks for Elderly-Cohort will be developed; this report will include pivotal consideration on
 - a. an analysis of safety issue in the three elderlies-arms
 - b. a preliminary analysis of immunogenicity in the three elderlies-arms aimed at identifying the most convenient doses to be used in the eventual phase 2/3 trial.
 - c. comparison of safety and immunogenicity between adults and elderlies (across the cohort comparison) to define the most convenient doses to be used either in general population or special groups at risk.
- 3. Within one year since study approval final report will be produced including:
 - a. Final analysis on safety and immunogenicity at 24 weeks after vaccination in Adults-Cohort
 - b. Final analysis on safety and immunogenicity at 24 weeks after vaccination in Elderlies-Cohort

[figure not shown]

Figure 6 Estimated time (week) for enrollment and follow-up for Adults-Cohort. Figures within cells represent time (in weeks) after vaccination. Grey bars represent timing of authorization for enrollment. Blue cells represent time of participants' enrollment. Emerald green cells represent time for safety assessment. Golden cells represent time of sampling carried out for immunogenicity assay on frozen specimens. Red cells represent time of sampling carried out for immunogenicity assay on fresh samples. Orange cells represent milestones (letters represent the specific milestone). Olive green cells represent deliverables (numbers represent the specific deliverable).

[figure not shown]

Figure 7 Estimated time (week) for enrollment and follow-up for Elderlies-Cohort. Figures within cells represent time (in weeks) after vaccination Grey bars represent timing of authorization for enrollment. Blue cells represent time of participants' enrollment. Emerald green cells represent time for safety assessment. Golden cells represent time of sampling carried out for immunogenicity assay on frozen specimens Red cells represent time of sampling carried out for immunogenicity assay on fresh samples. Orange cells represent milestones (letters represent the specific milestone). Olive green cells represent deliverables (numbers represent the specific deliverable).

5. Study design

This is a *first-in-human*, open-label, dose escalation, phase 1A/1B clinical trial to assess the safety and immunogenicity of the candidate GRAd-COV2 vaccine in healthy volunteers aged 18-55 years and elderly volunteers aged 65-85 years. The vaccine will be administered intramuscularly once in time.

We aim to enroll 90 patients in two cohorts with three arms each (i.e. 15 participants per arm in six arms). Each of the study arm will assess a unique dose of the candidate GRAd-COV2 in a particular population, either adults or elderlys.

- Adults-Cohort (Phase 1A):
 - Arm-1 will investigate safety and immunogenicity of a dose of 5×10^{10} viral particles in adults.
 - Arm-2 will investigate safety and immunogenicity of a dose of 1×10^{11} viral particles in adults.
 - Arm-3 will investigate safety and immunogenicity of a dose of 2×10^{11} viral particles in adults.
- Elderlies-Cohort (Phase 1B)
 - Arm-4 will investigate safety and immunogenicity of a dose of 5×10^{10} viral particles in elderlys.
 - Arm-5 will investigate safety and immunogenicity of a dose of 1×10^{11} viral particles in elderlys.
 - Arm-6 will investigate safety and immunogenicity of a dose of 2×10^{11} viral particles in elderlys.

To minimize the risk of severe adverse event in frail subjects enrollment of Elderlies-cohort will start after that 4-week safety results in Adults-Cohort will be available. Moreover, as it is a first in human trial, we have scheduled volunteers to be enrolled according to a strict frame of authorization rules. In particular, each arm includes two groups (A and B). Group As are made of 3 volunteers each to be enrolled throughout a week. The occurrence of SAE within 48h since the injection will be reported to data safety monitoring board (DSMB) and the enrolment suspended until a direct effect of the vaccination is excluded. Group Bs are made of 12 participant each to be enrolled over a week. DSMB provide binding advice on sequential enrollment across groups and arms; this is:

- enrolment of Arm-1 group B and Arm-2 group A is bound to a positive decision on 7-day safety of Arm-1 group A;
- enrolment of Arm-2 group B and Arm-3 group-A is bound to a positive decision on 7-day safety of Arm-2 group A;
- enrolment of Arm-3 group B is bound to a positive decision on 7-day safety of Arm-3 group A;
- enrolment of Arm-4 group A is bound to a positive decision on 4-week safety Arm-1;
- enrolment of Arm-4 group B and Arm-5 group A is bound to a positive decision on 7-day safety of Arm-4 group A;
- enrolment of Arm-5 group B and Arm-6 group-A is bound to a positive decision on 7-day safety of Arm-5 group A;
- enrolment of Arm-6 group B is bound to a positive decision on 7-day safety of Arm-5 group A.

Figure 8 reports the flow-charts for authorization and enrollment.

[figure not shown]

Figure 8 Study design and enrollment flow charts according to DSMB binding decisions

6. Recruitment and withdrawal

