7.7. Vaccination sequence

For safety reasons enrolment of *first in human* vaccine administration will be carried out on a weekly sequence in the six different arms. Each arm will be divided into 2 groups. Group-A are made of 3 volunteers each and group-Bs are made of 12 volunteers each.

At the beginning of the study clinical center will smoothly screen eligible subjects.

At enrollment on day 1 the first participant (arm 1 group-A) will be vaccinated ahead of any other participants and the profile of adverse events will be reviewed 48 hours after vaccination. Provided there are no safety concerns, as assessed by the local medical investigators, another two participants will be vaccinated at the same dose after at least 48 hours has elapsed following the first participant. Thus within one week, three participants will be vaccinated.

The following week the three participants vaccinated will undergo clinical screening for AE including a medical visit and a laboratory tests up to 7 days after vaccination. DSMB will analyze data on safety for arm 1 group-A and provide binding advice for the eventual enrolment. Eventual enrollment will include two blocks of participants this is:

- A. Arm 1 group-B (12 participants)
- B. Arm 2 group-A (3 participants)

Participants in arm 2 group-A will be scheduled for vaccination similarly to those vaccinated in arm 1 group-A, 48 hours apart from each other, provided there are no safety concerns, as assessed by the local medical investigators. Participants in arm 1 group-B will be smoothly vaccinated throughout the week.

The participants vaccinated in arm 2 group-A and arm-1 group-B undergo clinical screening for AE including a medical visit and a laboratory tests up to 7 days after vaccination. DSMB will analyze data on safety for arm 2 group-A and provide binding advice for the eventual enrolment. Eventual enrollment will include two blocks of participants this is:

- A. Arm 2 group-B (12 participants)
- B. Arm 3 group-A (3 participants)

Participants in arm 3 group-As will be scheduled for vaccination similarly to those vaccinated other group-As, 48 hours apart from each other, provided there are no safety concerns, as assessed by the local medical investigators. Participants in arm 2 group-B will be smoothly vaccinated throughout a week.

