#### 4.11.7 Safety Monitoring (Data and Safety Monitoring Board [DSMB])

The main roles of the DSMB for this study will be:

- decision-making on dose escalation, escalation intervals and cohort extension (if applicable).
- Monitoring all safety data recorded while the study is on-going.
- Proposing changes in the design and operations of the trial during the course of the study. For documented safety reasons, the DSMB can suggest and discuss with the Sponsor the interruption of the study. In case this decision will be agreed, the Sponsor should ensure the interruption in a reasonable timeframe, complying with ICH-GCP and all applicable Regulations.

The justification for the establishment of the DSMB and the grounds for dose escalation, as well as the DSMB procedures is provided in the DSMB charter.

Seven DSMB meetings are planned prospectively, in order to:

- DSMB authorizes ARM1 group B and ARM2 Group A
- DSMB authorizes ARM2 group B and ARM3 Group A
- DSMB authorizes ARM3 group B
- DSMB revises 4-week safety of whole Arm-1. DSMB authorize enrollment in ARM4 Group A.
- DSMB authorizes ARM4 Group B and ARM5 Group A
- DSMB authorize ARM5 Group B and ARM6 Group A
- DSMB authorize ARM6 Group B

Tables, listings, and figures (TLFs) provided for the DSMB are created by the Parexel statistical team. All TLFs (planned and ad-hoc) created for the DSMB are developed following the guidelines defined in this SAP, as appropriate. Specifications for these outputs are included in a separate TLF shells dedicated to solely supports the review conducted by the DSMB.

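### At the gates opening Arm-3 and Arm-6 (and expanding them), the named safety data are three sentinels; the documents do not say whether the concurrent 12-person lower-dose group B belongs to the decision

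*Protocol*

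**What the plan says.** Protocol section 5 splits each arm into two groups: "Group As are made of 3 volunteers each to be enrolled throughout a week" and "Group Bs are made of 12 participant each to be enrolled over a week". Enrolment then passes through DSMB gates. The first reads "enrolment of Arm-1 group B and Arm-2 group A is bound to a positive decision on 7-day safety of Arm-1 group A". The second reads "enrolment of Arm-2 group B and Arm-3 group-A is bound to a positive decision on 7-day safety of Arm-2 group A". SAP 3.1 repeats the same groups gate by gate.

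Section 7.7 describes the 7-day check in the step before the second gate: "The participants vaccinated in arm 2 group-A and arm-1 group-B undergo clinical screening for AE including a medical visit and a laboratory tests". The next sentence is "DSMB will analyze data on safety for arm 2 group-A and provide binding advice for the eventual enrolment". Arm-1 group B appears in the first sentence and not in the second. The step before Arm-6 opens is described in the same way, with Arm-4 group B checked alongside Arm-5 group A.

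SAP 4.11.7 describes the DSMB's role more widely, as "Monitoring all safety data recorded while the study is on-going". It refers to the DSMB charter for the grounds for dose escalation and to separate table shells for DSMB outputs. Neither was available for this review, and Figure 8 (the enrolment flow chart) is not shown.

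**The concern.** In a first-in-human escalation, the decision to open the highest dose is tied by name to three people. Twelve more at a lower dose are having the same visit and laboratory tests in the same step. The protocol treats lower-dose data as relevant elsewhere: the halting rules in section 9.8 carry a halt at one dose to the next higher one. It can also define a review set when it chooses to. Entry to the elderly cohort rests on 4-week data for the whole of Arm-1, with at least 12 of 15 complete. The 7-day gates have no comparable statement.

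At stake is whether non-halting group B findings count in the recorded decision. This arises when the highest dose is first given to adults, and again at ages 65-85.

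**Working it through.** **Sizes.** Section 5 gives 3 + 12 = 15 per arm, and 6 × 15 = 90, which reproduces the total in section 10.1. The plan gives no detection probability for any gate, so there is none to reproduce.

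**Gate by gate.** The last column is the size of the named group over the number vaccinated so far in that cohort.

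| Gate | Named in section 5 and SAP 3.1 | Named in section 7.7 | Lower-dose group B in the same step | Named / vaccinated |
|---|---|---|---|---|
| 1B + 2A | Arm-1 A | Arm-1 A | none | 3/3 |
| 2B + 3A | Arm-2 A | Arm-2 A | Arm-1 B (12) | 3/18 |
| 3B | Arm-3 A | Arm-2 A | Arm-2 B (12) | 3/33 |
| 4A | whole Arm-1, 4 weeks | same, at least 12 of 15 | not applicable | not three-person |
| 4B + 5A | Arm-4 A | Arm-4 A | none | 3/3 |
| 5B + 6A | Arm-5 A | Arm-4 A | Arm-4 B (12) | 3/18 |
| 6B | Arm-5 A | Arm-5 A | Arm-5 B (12) | 3/33 |

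Counts: 3 + 12 + 3 = 18, and 18 + 12 + 3 = 33. The pattern holds at two of the four gates that open a higher dose within a cohort (3A and 6A, not 2A and 5A), and at four of seven gates overall. The table also shows sections 5 and 7.7 naming different groups at 3B and at 5B + 6A. At 6B both name Arm-5 group A, so no Arm-6 data are named.

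**Is group B complete in time?** With sentinels 48 hours apart, on days 0, 2 and 4 at the earliest, their 7-day data are complete on day 4 + 7 = 11. If 12 vaccinations are spread evenly, those given by day 4 are also complete by day 11:
- over 5 days, 12 of 12;
- over 6 days, 10 of 12;
- over 7 days, 9 of 12 (11 of 12 if the Week 1 visit uses its -1 day window).

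The named three are then 3/15 = 20% to 3/12 = 25% of same-step participants with complete data.

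**Detection.** The documents give no event rates, so these are assumptions. P(at least one event) = 1 − (1 − p)^n:

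| Assumed rate p | n = 3 | n = 15 |
|---|---|---|
| 5% | 14.3% | 53.7% |
| 10% | 27.1% | 79.4% |
| 20% | 48.8% | 96.5% |

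After zero events, the one-sided 95% upper limit is 1 − 0.05^(1/n): 63.2% for n = 3 and 18.1% for n = 15. The n = 15 figures pool two dose levels under one common rate. At the 3A gate the 15 are 3 at 1×10^11 vp and 12 at 5×10^10 vp. The number at the dose just below the one being opened remains 3.

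**What the halting rules catch.** Take a type of event that counts under rule A or B only when seen twice in a group, at an assumed 10% rate. In 12 people:
- exactly one: 12 × 0.1 × 0.9^11 = 37.7%;
- two or more: 1 − 0.9^12 − 0.377 = 34.1% (in 3 people, 2.8%).

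Group B can therefore block escalation through section 9.8, but a single such event does not.

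**The case against.** The strongest reply is that a named minimum condition and a general duty to monitor everything are compatible. Section 7.7 does not say the DSMB looks at nothing else. Under section 9.5 it receives SAEs within 48 hours and AEs within 7 days. Under section 13.1 it meets weekly during enrolment and can withhold enrolment. A reader might infer that group B signals are lost to the DSMB; the documents do not support that.

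The halting rules also cover more than the two-event rules suggest. Rule D halts on one related serious event. Section 9.1 counts any hospitalization, significant medical intervention and grade 3 or higher safety blood abnormalities as serious. Section 9.2 describes a severe solicited reaction as one needing invasive intervention or hospitalization. A reader might infer that any single severe reaction in group B goes unheeded; on these definitions most such reactions, if judged related, would halt enrolment.

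All of this stands, and it narrows the point. The remainder is events graded severe by measurement alone in Table 1 (for example one fever above 39.0), severe non-serious solicited reactions starting later than the day after vaccination, moderate reactions in any number, and laboratory changes below grade 3. The 7-day AE reporting limit also allows a late group B event to arrive after the gate meeting. Receiving reports is not the same as including them in the recorded decision.

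A further reply is that the 12 are not at the dose just below the next step. That is correct, and the added data are lower-dose information only. Finally, the charter may already define a cumulative review set. If so, sections 5 and 7.7 and SAP 3.1 need only be aligned with it.

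**Conclusion.** The point holds at the gates opening Arm-3 and Arm-6, and at the expansion gates 3B and 6B. There the stated criterion names one three-person group while a 12-person lower-dose group B, with about 9 to 12 complete, has its 7-day check in the same step. At the two dose-opening gates the named data are 3 of 18 vaccinated in the cohort.

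A reader might infer that every escalation decision has this gap. It does not: at 2A and 5A no group B in that cohort has yet been vaccinated, and the 4A gate uses the whole of Arm-1. Nor do the figures of 27% against 79%, or 63% against 18%, describe better knowledge of one dose; they rest on assumed rates common to two doses.

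The gap is confined to non-serious, sub-halting reactions and laboratory changes in group B. The DSMB may see them, but the stated criterion does not include them. It is a modest weakness that should be corrected because the data are already collected. The unseen charter, DSMB shells and Figure 8 could narrow it further.

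**What to change.** 1. Reconcile Protocol sections 5 and 7.7, SAP 3.1, SAP 4.11.7 and the DSMB charter on the data reviewed at each gate, including which arm and group is reviewed where the passages differ (3B and 5B + 6A) and whether the group named at 6B is the one intended.
2. Make the milestone DSMB tables cumulative over all participants vaccinated to date, by dose and age cohort, with each person's 7-day status marked complete or pending.
3. State in sections 5 and 7.7 that the recorded decision refers to that set.

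This needs no new visit or test. Marking pending cases means no wait is imposed. What counts as a positive decision stays with the sponsor and the DSMB. The cost is wording in the listed sections and a little extra DSMB table work.

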The participants vaccinated in arm 3 group-A and arm 2 group-B will undergo clinical screening for AE including a medical visit and a laboratory tests up to 7 days after vaccination. DSMB will analyze data on safety for arm 2 group-A and provide binding advice for the eventual enrolment. Eventual enrollment will include one block of participants this is:

- A. Arm 3 group-B (12 participants)

Participants in arm 3 group-B will be smoothly vaccinated throughout the week.

The participants vaccinated in arm 3 group-b will undergo clinical screening for AE including a medical visit and a laboratory tests up to 7 days after vaccination. DSMB will analyze data and provide a general advice on vaccine safety at the conclusion of enrollment of the Adult-Cohort.

When data on 4-week safety for the whole arm 1 (15 participants) will be available. DSMB will provide binding advice for the eventual enrolment in the Elderlies-Cohort. The decision will be done only if no less than full data of 12 out of 15 participants will be available.

The enrollment the Elderlies-Cohort will follow the same scheme of the enrollment of Adults-Cohort.

The first participant of the Elderly-Cohort (arm 4 group-A) will be vaccinated ahead of all other elderlies participants. Provided there are no safety concerns, as assessed by the local medical investigators, another two participants will be vaccinated at the same dose after at least 48 hours has elapsed following the first participant. By the end of a week, three participants will be vaccinated.

All the participants vaccinated in ARM 4 group-A will undergo clinical screening for AE including a medical visit and a laboratory tests up to 7 days after vaccination. DSMB will analyze data on safety for arm 4 group-A and provide binding advice for the eventual enrolment. Eventual enrollment will include two blocks of participants this is:

- A. Arm 4 group-B (12 participants)
- B. Arm 5 group-A (3 participants)

Participants in arm 5 group-A will be scheduled for vaccination similarly to those vaccinated group-As, 48 hours apart from each other, provided there are no safety concerns, as assessed by the local medical investigators. Participants in arm 4 group B will be smoothly vaccinated throughout the week.

The participants vaccinated in arm 5 group-A and those vaccinated in arm 4 group-B will undergo clinical screening for AE including a medical visit and a laboratory tests up to 7 days after vaccination. DSMB will

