analyze data on safety for arm 4 group-A and provide binding advice for the eventual enrolment. Eventual enrollment will include two block of participants this is:

- A. Arm 5 group-B (12 participants)
- B. Arm 6 group-A (3 participants)

Participants in arm 6 group-A will be scheduled for vaccination similarly to those vaccinated group-As, 48 hours apart from each other, provided there are no safety concerns, as assessed by the local medical investigators. Participants in arm 5 group B will be smoothly vaccinated throughout the week.

The participants vaccinated in arm 5 group-A and those vaccinated in arm 5 group-B will undergo clinical screening for AE including a medical visit and a laboratory tests up to 7 days after vaccination. DSBM will analyze data on safety for arm 5 group-A and provide binding advice for the eventual enrolment. Eventual enrollment will include one block of participants this is:

- A. Arm 6 group-B (12 participants)

Participants in arm 3 group-B will be smoothly vaccinated throughout the week.

The participants vaccinated in arm 6 group-B clinical screening for AE including a medical visit and a laboratory tests up to 7 days after vaccination. No more participants will be vaccinated.

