### Elderlies-Cohort (Phase 1B)

Arm-4 will investigate safety and immunogenicity of a dose of 5xE10 vp in elderlies.

Arm-5 will investigate safety and immunogenicity of a dose of 1xE11 vp in elderlies.

Arm-6 will investigate safety and immunogenicity of a dose of 2xE11 vp in elderlies.

vp: Viral particles

To minimize the risk of severe adverse events in frail subjects, enrollment of Elderlies-Cohort will start after that 4-week safety results in Adults-Cohort will be available. Moreover, as it is a first in human trial, we have scheduled volunteers to be enrolled according to a strict frame of authorization rules. In particular, each arm includes two groups (A and B). Group As are made of 3 volunteers each to be enrolled throughout a week. The occurrence of SAE within 48h since the injection will be reported to data safety monitor board (DSMB) and the enrolment suspended until a direct effect of the vaccination is excluded. Group Bs are made of 12 volunteer each to be enrolled over a week. DSMB provide advice on sequential enrollment across groups and arms; this is:

- Enrolment of Arm-1 group B and Arm-2 group A is bound to a favorable 7-day safety profile in Arm-1 group A;
- Enrolment of Arm-2 group B and Arm-3 group-A is bound to a favorable 7-day safety profile in Arm-2 group A;
- Enrolment of Arm-3 group B is bound to favorable 7-day safety profile in Arm-3 group A;
- Enrolment of Arm-4 group A is bound to a favorable 4-week safety profile in the whole Arm- 1;
- Enrolment of Arm-4 group B and Arm-5 group A is bound to a favorable 7-day safety profile in Arm-4 group A;
- Enrolment of Arm-5 group B and Arm-6 group-A is bound to a favorable 7-day safety profile in Arm-5 group A;
- Enrolment of Arm-6 group B is bound to a favorable 7-day safety profile in Arm-5 group A.

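### Release of the 12 Arm-6 group B participants is tied to the Arm-5 sentinels, so no visible rule requires 7-day review of the Arm-6 sentinels

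*Protocol*

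**What the plan says.** Protocol section 5 splits every arm into group A (3 people) and group B (12 people) and makes enrolment depend on seven binding DSMB decisions. The last reads "enrolment of Arm-6 group B is bound to a positive decision on 7-day safety of Arm-5 group A". SAP section 3.1 repeats it: "Enrolment of Arm-6 group B is bound to a favorable 7-day safety profile in Arm-5 group A".

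Protocol section 7.7 tells the same sequence as a narrative. For the decision that releases Arm-6 group B it says "DSBM will analyze data on safety for arm 5 group-A and provide binding advice for the eventual enrolment". The follow-up described just before that decision is: "The participants vaccinated in arm 5 group-A and those vaccinated in arm 5 group-B will undergo clinical screening for AE". Arm-6 group A does not appear there.

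The matching adult rule in section 5 is "enrolment of Arm-3 group B is bound to a positive decision on 7-day safety of Arm-3 group A", and section 7.7 says of the older cohort: "The enrollment the Elderlies-Cohort will follow the same scheme of the enrollment of Adults-Cohort".

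Section 7.7 differs from section 5 at two other decisions. For Arm-3 group B it has "DSMB will analyze data on safety for arm 2 group-A and provide binding advice for the eventual enrolment. Eventual enrollment will include one block". For Arm-5 group B with Arm-6 group A it has "analyze data on safety for arm 4 group-A and provide binding advice for the eventual enrolment. Eventual enrollment will include two block".

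**The concern.** A sentinel group is useful only if its data are seen before more people of the same age get the same dose. In section 5 and SAP 3.1 the last two conditions are identical: 7-day safety of Arm-5 group A releases the Arm-6 sentinels, and the same finding then satisfies the rule for the remaining 12 people in Arm-6. The sentinel step at the top dose in the older cohort then has no required role in the decision it exists to inform.

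The wrong group is named in three places, and SAP version 4.0 still carries it. The conflicts between sections 5 and 7.7 add a second problem: a site or DSMB member working from one section would apply different binding rules from someone working from the other.

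**Working it through.** The plan gives no sample size, power or alpha figure for this point, so there is nothing of that kind to reproduce. The check is a comparison of the release rules.

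**Inputs.** Group sizes of 3 and 12 in six arms (protocol sections 5 and 7.7): 6 × (3 + 12) = 90, which matches the planned total. Doses: 5×10^10, 1×10^11 and 2×10^11 vp.

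**Data named for each decision.** The third column applies the adult pattern to both cohorts.

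| Decision | Releases | Expected | Section 5 and SAP 3.1 | Section 7.7 |
|---|---|---|---|---|
| 1 | 1B, 2A | 1A | 1A | 1A |
| 2 | 2B, 3A | 2A | 2A | 2A |
| 3 | 3B | 3A | 3A | **2A** |
| 4 | 4A | Arm-1, 4 weeks | Arm-1, 4 weeks | Arm-1, 4 weeks |
| 5 | 4B, 5A | 4A | 4A | 4A |
| 6 | 5B, 6A | 5A | 5A | **4A** |
| 7 | 6B | 6A | **5A** | **5A** |

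**Counts.** Group B totals 6 × 12 = 72.
- Section 5 and SAP 3.1: 1 of 7 decisions is wrong. It covers 12 people; 12/72 = 16.7%.
- Section 7.7 read literally: 3 of 7 decisions are wrong. They cover 3B, 5B and 6B, so 3 × 12 = 36; 36/72 = 50%.
- Dose step for the Arm-6 sentinels: 2×10^11 / 1×10^11 = 2 if they follow Arm-5 group A, but 2×10^11 / 5×10^10 = 4 if they follow Arm-4 group A, as section 7.7 says.

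**Do other rules require the missing review?**
- Milestone G (protocol 4.2.4, repeated in SAP 4.11.7) is a separate authorisation for Arm-6 group B, but names no data.
- The DSMB meets weekly during enrolment (13.1) and receives AE reports within 7 days (9.5). Neither provision makes release wait for complete 7-day data on Arm-6 group A.
- The suspension for events within 48 hours of injection (section 5) applies to SAEs only.
- Halting rules A and B (9.8) need the same severe solicited event in at least two vaccinees of a group, starting on the day of vaccination or the next day. One sentinel with fever above 39.0 °C (severe in Table 1), or such a fever starting on days 3-7, meets no halting rule unless it is also a related SAE.

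**What three sentinels can show (illustration).** The documents give no rate of severe reactions, so the rates p below are assumed. P(at least one) = 1 − (1 − p)^3. P(at least two) = 3p²(1 − p) + p³.

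| Assumed p | At least one of 3 | At least two of 3 |
|---|---|---|
| 10% | 27% | 3% |
| 20% | 49% | 10% |
| 30% | 66% | 22% |
| 50% | 88% | 50% |

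A review of the sentinels would see a single event. A two-event rule often would not fire.

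**The case against.** The strongest reply is that the intent can be recovered and the sentinels are not unwatched. The older cohort is said to follow the adult scheme. Milestones F and G are separate, and G would be redundant if Arm-5 data were enough. Section 7.7 otherwise pairs the new arm's group A with the previous arm's group B before such decisions, so naming two Arm-5 groups looks like a one-digit typo. All this is fair evidence of intent. It does not supply a rule, because the specific binding condition says otherwise and section 7.7 misnames the adult decision it would be copied from.

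The safeguards are also wider than halting rules A and B. Arm-6 sentinels are vaccinated 48 hours apart. The local investigator may hold the study (9.7). Hospital admission, even as a precaution, and any grade 3 or higher safety blood result count as SAEs (9.1), and one related SAE meets halting rule D. Severe solicited reactions as defined in 9.2 involve hospitalisation or invasive intervention, so many would be caught. That narrows the gap mainly to events managed outside hospital and graded severe by Table 1, such as fever. It does not close it, and the local hold is discretionary.

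Adults in Arm-3 receive the same top dose, which gives some reassurance but does not replace sentinels aged 65-85. Finally, decisions 3 and 6 are plainly slips: the follow-up sentence before each names the right sentinels. The 50% and the fourfold step therefore describe a literal reading of section 7.7 only. Figures 7 and 8 and the DSMB charter cannot be seen and may be correct; if so, the text contradicts them and still needs correcting.

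**Conclusion.** The concern holds and must be fixed. In every visible statement of the rule, Arm-6 group B is released on the wrong sentinels: 12 people aged 65-85 at the highest dose, 12 of the 15 in that arm. Section 7.7 also contradicts section 5 on two further decisions. The counts measure who is covered by each wording; they do not predict harm. The defect is a missing explicit requirement, not an absence of monitoring, and no analysis or sample size changes. The conclusion assumes that the adult pattern was intended for both cohorts, and it is limited to the text that can be seen.

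**What to change.** - In protocol sections 5 and 7.7 and SAP section 3.1, make release of Arm-6 group B depend on 7-day safety of Arm-6 group A.
- In section 7.7, have the follow-up sentence before that decision name Arm-6 group A and Arm-5 group B. In the vaccination sentence after it, change Arm-3 group B to Arm-6 group B.
- In section 7.7, make Arm-3 group B depend on Arm-3 group A, and make Arm-5 group B and Arm-6 group A depend on Arm-5 group A.
- Minor: the lead-in in section 5 and SAP 3.1 refers to 4-week results in the whole adult cohort, while the operative rule is Arm-1. Align the two.
- Check that Figure 8 and the DSMB charter state the same seven conditions.
- SAP version 4.0 dates from June 2021, so releases may already have happened. If so, record which data each DSMB decision used, especially decisions 3, 6 and 7.

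The cost is text corrections and a document check. The D2 and W1 visits already collect the data, so no participants, visits or samples are added. At most, Arm-6 group B waits for its sentinels' 7-day data, as Arm-3 group B does in section 5.
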